## 4.3.3 Rationale for Dose Selection/Regimen/Modification

### 4.3.3.1 Pembrolizumab Dose

The planned dose of pembrolizumab for this study is 200 mg Q3W. Based on the totality of data generated in the Keytruda development program, 200 mg Q3W is the appropriate dose of pembrolizumab for adults across all indications and regardless of tumor type. As outlined below, this dose is justified by:

- Clinical data from 8 randomized studies demonstrating flat dose- and exposure-efficacy relationships from 2 mg/kg Q3W to 10 mg/kg every 2 weeks (Q2W),
- Clinical data showing meaningful improvement in benefit-risk including OS at 200 mg Q3W across multiple indications, and
- Pharmacology data showing full target saturation in both systemic circulation (inferred from pharmacokinetic [PK] data) and tumor (inferred from physiologically-based PK [PBPK] analysis) at 200 mg Q3W

Among the 8 randomized dose-comparison studies, a total of 2262 subjects were enrolled with melanoma and NSCLC, covering different disease settings (treatment naïve, previously treated, PD-L1 enriched, and all-comers) and different treatment settings (monotherapy and in combination with chemotherapy). Five studies compared 2 mg/kg Q3W versus 10 mg/kg Q2W

# Proprietary Information of MD Anderson

Protocol # 2016-0251

Date: February 24, 2020

30

(KEYNOTE [KN]001 Cohort B2, KN001 Cohort D, KN002, KN010, and KN021), and 3 studies compared 10 mg/kg Q3W versus 10 mg/kg Q2W (KN001 Cohort B3, KN001 Cohort F2 and KN006). All of these studies demonstrated flat dose- and exposure-response relationships across the doses studied representing an approximate 5- to 7.5 fold difference in exposure. The 2 mg/kg (or 200 mg fixed-dose) Q3W provided similar responses to the highest doses studied. Subsequently, flat dose-exposure-response relationships were also observed in other tumor types including head and neck cancer, bladder cancer, gastric cancer and classical Hodgkin Lymphoma, confirming 200 mg Q3W as the appropriate dose independent of the tumor type. These findings are consistent with the mechanism of action of pembrolizumab, which acts by interaction with immune cells, and not via direct binding to cancer cells.

Additionally, pharmacology data clearly show target saturation at 200 mg Q3W. First, PK data in KN001 evaluating target-mediated drug disposition (TMDD) conclusively demonstrated saturation of PD-1 in systemic circulation at doses much lower than 200 mg Q3W. Second, a PBPK analysis was conducted to predict tumor PD-1 saturation over a wide range of tumor penetration and PD-1 expression. This evaluation concluded that pembrolizumab at 200 mg Q3W achieves full PD-1 saturation in both blood and tumor.

Finally, population PK analysis of pembrolizumab, which characterized the influence of body weight and other subject covariates on exposure, has shown that the fixed-dosing provides similar control of PK variability as weight based dosing, with considerable overlap in the distribution of exposures from the 200 mg Q3W fixed dose and 2 mg/kg Q3W dose. Supported by these PK characteristics, and given that fixed-dose has advantages of reduced dosing complexity and reduced potential of dosing errors, the 200 mg Q3W fixed-dose was selected for evaluation across all pembrolizumab protocols..

### 4.3.3.2 Zepatier (Grazoprevir and Elbasvir) Dose and Duration

Zepatier is a combination of 2 oral agents. The Zepatier dose regimen is as described in the prescribing information.

A grazoprevir dose of 100 mg qday was selected for Phase 3 trials based on high efficacy and a good safety profile from the Phase 2 dose ranging studies PN003 and PN038, as well as from PN035 and PN039. For detailed information, please refer to the IB.

An elbasvir dose of 50 mg qday was selected for Phase 3 trials based on high efficacy and a good safety profile from a Phase 1b monotherapy study in HCV infected subjects, elbasvir PN002, and a Phase 2a dose ranging study, grazoprevir PN035. For detailed information, please refer to the IB.

Zepatier was approved based upon 2 placebo controlled trials and 4 uncontrolled trials (49-53). The trials were Phase II or Phase III studies of patients with HCV GT1, GT4, and GT6 with compensated liver disease with and without cirrhosis. The names of the trials include C-EDGE, C-Surfer, C-Scape, and C-Salvage. In these studies Zepatier was given for 12 to 18 weeks with and without RBV. Zepatier was administered qday PO in these trials with the doses of 50 mg elbasvir and 100 mg grazoprevir. For subjects who received RBV, the RBV dosage was weight-

based (less than 66 kg = 800 mg per day, 66 to 80 kg = 1000 mg per day, 81 to 105 kg = 1200 mg per day, greater than 105 kg = 1400 mg per day) administered PO in two divided doses with food. Sustained virologic response was the primary endpoint in all trials and was defined as HCV RNA less than the LLOQ at 12 weeks after the cessation of treatment (SVR12).

### 4.3.3.3 Ribavirin Dose and Duration

The dose and duration of RBV with Zepatier for HCV GT1a: treatment-naïve with baseline NS5A polymorphisms was established in the C-Worthy trial (57,58). See Zepatier prescribing information. For patients with a creatinine clearance (CrCl) greater than 50 mL per minute, the recommended dosage of RBV is weight-based (less than 66 kg = 800 mg per day, 66 to 80 kg = 1000 mg per day, 81 to 105 kg = 1200 mg per day, greater than 105 kg = 1400 mg per day) administered in two divided doses with food. For patients with CrCl less than or equal to 50 mL per minute, including patients receiving hemodialysis, refer to the RBV tablet.

## 4.3.4 Rationale for Endpoints

### 4.3.4.1 Primary Endpoints

#### 4.3.4.1.1 Safety

This is a study to estimate the safety and tolerability of the combination of pembrolizumab and Zepatier with or without ribavirin in subjects with advanced HCC treated previously with systemic monotherapy with sorafenib. Safety parameters commonly used for evaluating investigational systemic anticancer treatments are included as safety endpoints including, but not limited to, the incidence of, causality, and outcome of AEs/SAEs; and changes in vital signs and laboratory values. Adverse events will be assessed as defined by the NCI CTCAE, Version 4.0.

#### 4.3.4.1.2 Sustained Virologic Response

The goal of therapy for chronic HCV infection is eradication of the virus, which is typically measured as a SVR. Obtaining clinical outcomes from prospective, randomized, controlled clinical trials in drug development programs for chronic HCV infection is a challenge and not feasible for most HCC populations due to the difficulty of maintaining patients on a randomized arm without intervening therapy for a sufficient duration to identify late-occurring clinical events, such as hepatic decompensation or HCC. For many approvals, a virological surrogate (SVR) has been used to measure treatment success in clinical trials supporting approval. SVR is an objective endpoint that signifies long-term clearance of hepatitis C and is generally regarded as a “virological cure.” Based on numerous observational cohorts showing strong correlations between SVR and multiple clinically important outcomes, such as development of HCC, end-stage liver complications, and mortality, the FDA considers SVR a “validated” surrogate efficacy endpoint in CHC clinical trials (104-107).

Until recently, SVR at 24 weeks post-treatment (SVR24) has been considered the gold standard for treatment success; this end point is predictive of long-term eradication of the virus and

# Proprietary Information of MD Anderson

Protocol # 2016-0251

Date: February 24, 2020

32

correlates with a reduction in symptoms and in the rate of negative clinical outcomes (88). All HCV therapies approved by the US FDA to date have been based on the efficacy assessment of the proportion of patients attaining SVR24 in the phase III confirmatory studies. Most patients who achieved SVR24 maintain their serum-negative status for HCV RNA, and <1% of patients would have subsequent detectable HCV RNA after achieving SVR24 (96). SVR24 has been associated with a reduction in liver disease complications and improvement in survival (97-98), and has been accepted as the primary efficacy end point for HCV therapies for regulatory approval (99-101).

However, there is evidence that most patients who have an SVR at earlier time points (such as SVR12) maintain it until week 24 (SVR24) (103). For example from a large metaanalysis the positive predictive value (PPV) of SVR12 was 98% and the negative predictive value (NPV) was 99% for SVR24 among subjects with genotype 1 HCV infection. A similar level of concordance was observed for subjects with HCV genotype 2 or 3 infections, as well as in pediatric studies. About 2% of subjects who achieved an SVR12 subsequently relapsed by week 24 (did not achieve an SVR24). Furthermore, the treatment effect size (difference between treatment and active control arms) was similar for subjects with SVR12 and SVR24. The PPV of SVR4 was 91% and the NPV was 98% for SVR24 in subjects with genotype 1 HCV infection. SVR12 and SVR24 measurements were concordant in a large population of subjects with HCV infection who participated in clinical trials with various treatment regimens and durations (103) . The FDA examined the correlation between SVR12 and SVR24 in over 13,000 subjects pooled from multiple clinical trials of Peg-IFN-based regimens and found a high rate of concordance between SVR12 and SVR24; sensitivity and specificity for SVR12 were 99% and 98%, respectively. Therefore, the FDA has concluded that SVR12 is suitable as a primary endpoint for regulatory approval (89).

#### 4.3.4.2 Secondary/Exploratory Endpoints

This study will also utilize standard endpoints used in oncology studies. The secondary objectives of this study are to explore the anti-tumor efficacy or ORR per RECIST 1.1 criteria as assessed by M.D. Anderson radiology. Other secondary/exploratory endpoints will include DOR, DCR, TTP, PFS, and OS as assessed per RECIST 1.1.

- 1) ORR, defined as the proportion of subjects who have a CR or partial response (PR) using RECIST 1.1 and with confirmatory assessment as required per iRECIST at any time during the trial. Subjects with unknown or missing response information will be treated as non-responders.
- 2) DOR, defined in the subset of subjects with a CR or PR, based on RECIST 1.1 and with confirmatory assessment as required per iRECIST, as the time from first documented evidence of CR or PR until the first documented sign of PD or death due to any cause, whichever occurs first. Subjects who are alive, have not progressed, have not initiated new anti-cancer treatment, and have not been determined to be lost to follow-up are considered ongoing responders at the time of analysis.
- 3) PFS, defined as the time from the first dose of study treatment to the first

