# Proprietary Information of MD Anderson

Protocol # 2016-0251

Date: February 24, 2020

33

documented PD according to RECIST 1.1 and with confirmatory assessment as required per iRECIST, or death due to any cause, whichever occurs first. If a subject does not have a documented date of progression or death, PFS will be censored at the date of the last adequate assessment.

- 4) OS, defined as the time from the date of the first dose of study to the date of death due to any cause. Censoring will be performed using the date of last known contact for those who are alive at the time of analysis.
- 5) Viral resistance measurements will be made on any subject who had detectable virus above 1000 IU/mL after completing Zepatier therapy. Blood samples for viral resistance assays and the determination of the sequence of RAVs will be obtained.

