## 5.6.2 Treatment after Initial Radiologic Progression (iRECIST-based Management)

Immunotherapeutic agents such as pembrolizumab may produce antitumor effects by potentiating endogenous cancer-specific immune responses. The response patterns seen with such an approach may extend beyond the typical time course of responses seen with cytotoxic agents, and can manifest as a clinical response after an initial apparent increase in tumor burden (i.e., pseudoprogression) or even the appearance of new lesions. Standard RECIST-based assessment of disease progression may, thus, not provide an accurate assessment of response to immunotherapeutic agents such as pembrolizumab. For this reason, iRECIST has been developed to help guide treatment decisions during tumor immunotherapy.

For subjects who have initial radiological evidence of radiological PD by RECIST 1.1, the investigator may elect to continue a subject on study treatment until repeat imaging is obtained. This clinical judgment decision by the investigator should only be made if the subject is clinically stable, based on clinical factors including performance status, clinical symptoms, and laboratory data. Such subjects may continue to receive study treatment and an imaging-based tumor assessment should be repeated  $\geq 4$  weeks later in order to reassess PD per investigator assessment (Section 7.1.4.2.4).

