#### 8.4.1.2 Secondary Exploratory/Efficacy Endpoints

- ORR is defined as the proportion of the subjects in the analysis population who have a CR or PR. Responses are based on assessments by the blinded M.D. Anderson radiology per RECIST 1.1
- DOR is defined as the time from first response to disease progression in subjects who achieve a PR or better, based on assessments by the blinded M.D. Anderson radiology per RECIST 1.1.
- DCR is defined as the percentage of subjects who have achieved confirmed CR or PR or have demonstrated SD for at least 24 weeks prior to any evidence of progression, based on assessments by the blinded M.D. Anderson radiology per RECIST 1.1
- TTP is defined as the time from randomization to the first documented disease progression. If there is no documented disease progression, TTP is censored at last

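### The RECIST 1.1 response rate has no cut-off at first RECIST 1.1 progression and has iRECIST written into it, so a response first seen after progression can be counted

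*Combined protocol and SAP*

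**What the plan says.** **ORR.** Section 4.3.4.2, item 1, takes the proportion of subjects with a CR or PR "using RECIST 1.1 and with confirmatory assessment as required per iRECIST at any time during the trial". Section 8.4.1.2 says "ORR is defined as the proportion of the subjects in the analysis population who have a CR or PR", per RECIST 1.1, with no time window.

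**Duration of response (DOR).** Section 4.3.4.2, item 2, measures the "time from first documented evidence of CR or PR until the first documented sign of PD or death due to any cause". Section 8.4.1.2 says "DOR is defined as the time from first response to disease progression in subjects who achieve a PR or better".

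**Progression-free survival (PFS).** Section 4.3.4.2, item 3, uses "documented PD according to RECIST 1.1 and with confirmatory assessment as required per iRECIST".

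**Disease control rate.** In Section 8.4.1.2 this is the only response-rate endpoint with a limit tied to progression, and the limit is attached to stable disease: "have demonstrated SD for at least 24 weeks prior to any evidence of progression".

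**Which criteria apply.** Section 4.3.4.4 has iRECIST supporting the secondary as well as the exploratory response endpoints. Section 7.1.4.1.4 makes RECIST 1.1 the primary measure for response and for the date of progression. Table 17 labels DOR, time to progression (TTP) and PFS as RECIST 1.1. Section 8.4.1.3 keeps confirmed progression for the exploratory iRECIST endpoints.

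**After first progression.** For a clinically stable subject, Section 5.6.2 (treatment after initial radiologic progression) says "the investigator may elect to continue a subject on study treatment until repeat imaging is obtained". Section 7.1.4.1.5 puts the repeat scan 4 to 8 weeks later. Section 12.2 classes the first progression visit as iUPD, and later shrinkage that resolves it as iSD, iPR or iCR.

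**The concern.** A RECIST 1.1 response rate and an iRECIST response rate are kept apart by what happens after first RECIST 1.1 progression. Here the RECIST 1.1 definition does not stop at that progression, names iRECIST in its own wording, and sits in a trial that allows treatment and imaging to go on afterwards. An analyst following Sections 4.3.4.2 and 4.3.4.4 could count a late iPR in the secondary ORR; one following Sections 8.4.1.3 and 12.2 would not. No rule decides between them.

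Two things are at stake. Objectives 3.2(1) and 4.1(1) ask for two separate ORR estimates, and these can merge into one. Section 8.6.1 also turns on a single subject: no response in 15 means pembrolizumab is considered ineffective, and at least one is the signal for larger studies. If the only response comes after progression, the choice of window decides which statement is made, and that choice could be made after the data are seen.

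**Working it through.** **1. The plan's own figure.** Section 8.6.1 states that with 15 patients the chance of at least one response is more than 90% at a true rate of 15%.

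1 − (1 − 0.15)^15 = 1 − 0.85^15 = 0.913. This reproduces.

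**2. Can the two ORRs differ?** Section 12.2 states that there is no distinct iRECIST assessment before RECIST 1.1 progression, so the two sets of criteria can give different responses only after it. Section 8.4.1.3 changes only how progression is assessed and confirmed. The ORR definition in Section 8.4.1.2 does not mention progression, so that change need not alter ORR. With the window left open, the secondary and exploratory ORR can be the same number.

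**3. One subject under three readings.** Take RECIST 1.1 progression at the first scheduled scan (week 9, Section 7.1.4.1.2). A PR is first seen at a repeat scan 4 or 8 weeks later (Section 7.1.4.1.5), or at the next scheduled scan 9 weeks later, that is at week 13, 17 or 18.

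| Reading | Secondary ORR | DOR |
|---|---|---|
| A. Open window; first RECIST 1.1 progression is the event (Sections 7.1.4.1.4 and 8.4.1.3, Table 17) | Responder | 9 − 13 = −4, 9 − 17 = −8 or 9 − 18 = −9 weeks |
| B. Open window; progression must be confirmed per iRECIST (Section 4.3.4.2, item 3) | Responder | Week 9 is not an event; DOR runs forward from the PR and is not negative |
| C. The late response is only an iPR (Section 12.2) | Not a responder | Not applicable; counted only under Section 8.4.1.3 |

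Under A the same subject is a TTP and PFS event at week 9 and a responder afterwards. Table 18 has no row for progression dated before the response. Under B the endpoints labelled RECIST 1.1 use iRECIST progression. Under C there is no problem, but no sentence says that C applies.

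**4. Size.** Let q be the share of subjects whose only response follows RECIST 1.1 progression. The documents give no value, so q is assumed. If no subject responds before progression, closing the window gives 0 responders in 15. Leaving it open gives P(at least one) = 1 − (1 − q)^15:

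- q = 1%: 1 − 0.99^15 = 0.140
- q = 2%: 1 − 0.98^15 = 0.261
- q = 5%: 1 − 0.95^15 = 0.537

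If the pre-progression response rate is 5% (also assumed), the chance of meeting the signal is 1 − 0.95^15 = 0.537 with the window closed. With it open, the chance is 1 − (0.95 − q)^15:

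- q = 1%: 1 − 0.94^15 = 0.605
- q = 2%: 1 − 0.93^15 = 0.663
- q = 5%: 1 − 0.90^15 = 0.794

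Each such subject adds 1/15 = 6.7 percentage points to an arm's ORR.

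**The case against.** The strongest reply is that the plan already classifies the late response. Section 12.2 makes the first progression visit iUPD and the later shrinkage iPR or iCR, and Sections 4.3.4.3 and 8.4.1.3 give iRECIST its own endpoints. The open-ended phrase in the ORR definition may mean only that there is no fixed landmark visit. On this view nothing in the documents makes a post-progression response a RECIST 1.1 response.

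That stands against a stronger reading which a reader might infer: that every such subject is a RECIST 1.1 responder with a negative DOR. No passage says so. A negative DOR needs both an open ORR window and first, unconfirmed progression as the event, and the PFS definition in Section 4.3.4.2 ties iRECIST confirmation to progression. The reply does not remove the ambiguity, because the same section writes iRECIST into the secondary ORR and Section 4.3.4.4 applies it to the secondary response endpoints.

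Three further inferences also go too far:

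- **Using the 7% in Section 4.3.4.4 as the share.** It would give 1 − 0.93^15 = 66%. But it is pseudo-progression in melanoma, not response after progression, and Section 12.2 allows pseudo-progression to resolve to stable disease.
- **Calling the ORR biased against, or not comparable with, the 14.3% in Section 4.2.1.1.** That figure is for nivolumab, and the protocol does not say how responses after progression were handled there.
- **Saying that one late response settles development.** Section 8.6.1 also brings in the response profile, clinical benefit at 6 months, PFS and confidence intervals. The statement about ineffectiveness does, however, rest on the count alone.

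ORR is also a secondary estimation endpoint, and DOR is summarised only if numbers permit. Both are true, but Table 15 names ORR as the key efficacy analysis.

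**Conclusion.** The concern holds as an undefined response cut-off combined with a mixture of RECIST 1.1 and iRECIST. Following Section 4.3.4.2 can put a response first seen after RECIST 1.1 progression into the RECIST 1.1 ORR. The text then yields either a negative DOR (first progression as the event) or RECIST 1.1 endpoints that are iRECIST in substance (confirmed progression as the event). Such responses may occur; the documents do not show that they will.

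The size depends on an unknown share: 14%, 26% or 54% for at least one such subject in 15 at assumed shares of 1%, 2% or 5%, treating subjects as independent. The 6.7 points per subject and the crossing from no response to one response need no such assumption. The wording should be settled before analysis, because choosing the window after a late responder has appeared could determine whether the signal in Section 8.6.1 is met.

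**What to change.** 1. In Section 4.3.4.2, item 1, replace the open-ended time phrase that closes "using RECIST 1.1 and with confirmatory assessment as required per iRECIST at any time during the trial", and add the same sentence to Section 8.4.1.2, where that phrase does not occur: *RECIST 1.1 best overall response is taken from first dose to the first RECIST 1.1 progression or the start of new anticancer therapy, whichever is earlier; later responses count only in the iRECIST endpoints of Section 8.4.1.3.*
2. Remove the iRECIST-confirmation clause from the RECIST 1.1 definitions of ORR, DOR and PFS in Section 4.3.4.2.
3. Align Section 4.3.4.4, so that iRECIST supports the exploratory response endpoints and not the RECIST 1.1 secondary ones.
4. Use the same first RECIST 1.1 progression as the progression event for DOR and PFS. No RECIST 1.1 DOR can then be negative, and Table 18 needs no extra row for this case.

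The cost is a few sentences in the protocol and SAP, and possibly a slightly lower RECIST 1.1 ORR. The design figure of 0.913 at a 15% response rate is unchanged. Late responses are still reported, under iRECIST, and no rule on treatment or imaging changes.

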# Proprietary Information of MD Anderson

Protocol # 2016-0251

Date: February 24, 2020

33

documented PD according to RECIST 1.1 and with confirmatory assessment as required per iRECIST, or death due to any cause, whichever occurs first. If a subject does not have a documented date of progression or death, PFS will be censored at the date of the last adequate assessment.

- 4) OS, defined as the time from the date of the first dose of study to the date of death due to any cause. Censoring will be performed using the date of last known contact for those who are alive at the time of analysis.
- 5) Viral resistance measurements will be made on any subject who had detectable virus above 1000 IU/mL after completing Zepatier therapy. Blood samples for viral resistance assays and the determination of the sequence of RAVs will be obtained.

